#### 1.4 Preliminary Data

The work proposed here explores gut microbiota-targeted intervention as an early treatment for COVID-19. Gut microbiota contributes to the host immune homeostasis [20] and has already been implicated in the host's defense against respiratory viral infections [21, 22]. There is also some evidence for interactions between SARS-CoV-2 and the human gastrointestinal system: cell entry of SARS-CoV-2 requires the binding of the viral spike proteins to the angiotensin-converting enzyme 2 (ACE2) and this entry receptor is expressed in the small intestinal enterocytes [23, 24]; viral RNA was detected in 29% (44 of 153) of fecal specimens from a cohort of hospitalized COVID-19 patients and live virus was cultured in a subset of these samples [9]. In one study of 204 patients with COVID-19, almost 20% of the patients exhibited gastrointestinal symptoms (e.g. diarrhea, vomiting and abdominal pain) and these symptoms were more pronounced as disease severity increased [25].

Our intervention to mitigate COVID-19 focuses on promoting a select group of gut bacteria that ferment carbohydrates to produce beneficial SCFAs. In our clinical trials, a diet enriched with non-digestible but fermentable carbohydrates increased SCFA production and contributed to improved metabolic parameters [6, 26]. Importantly, we showed that the predominance of a select group of acetate and butyrate producers was associated with a concomitant reduction in pro-inflammatory and/or endotoxin-producing bacteria. Akin to tall trees in a forest, this group of carbohydrate-fermenting SCFA producers may constitute to a "Foundation Guild" of a healthy gut microbiota structure. In the context of acute respiratory viral infections, Sencio et al [13] showed that mice receiving fecal microbiota transplantation from influenza-infected animals exhibited compromised pulmonary immunity but were protected against bacterial superinfection by acetate supplementation. These data are consistent with our central hypothesis of a SCFA-producing Foundation Guild as the core of a healthy gut microbiota that are protective against complications associated with viral infections.

## 1.5 Sample Size Justification

We will enroll a total of 100 participants who have COVID-19-like symptoms and have positive/pending PCR-based COVID-19 test results. These individuals will be randomized into the control and treatment group in a 1:1 ratio (i.e. 50 participants/group). With the assumption of a positivity rate of 40-50% in symptomatic participants in the USF Carol & Frank Morsani Center for Advanced Healthcare drive-through testing center, we expect to have at least 20 confirmed COVID-19 cases in each group. We used the micropower R-package [27], in which the weighted Jaccard distance matrix was simulated based on within-group distance variance (mean and standard deviation) of data from 36 T2DM patients (unpublished data) to estimate the required sample size. Using the simulated matrices, the PERMANOVA powers are calculated for varying effect sizes ( $\omega^2$ ) and sample sizes. Our results show that 16 subjects per group afford 80% power to an  $\omega^2$  of 0.0106 which correspond to the difference ( $\omega^2$ =0.0120) between the control and treatment group with a similar high-fiber intervention in the T2DM patients (unpublished data). We therefore aim to recruit 20 confirmed COVID-19 cases in each group to allow for potential dropouts and/or incomplete sample/data sets from the participants.

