## **B.** Data Points

- Gut microbiota composition: fecal samples will be collected at Days 0, 28, 56 and the day when participants recover from COVID-19-like illness (if before Day 56)
- Clinical progress of COVID-19-like illness: 1) objective and subjective symptoms data will be collected twice a day from Day 1 to Day 28 or until they recover from COVID-19-like illness (whichever is later) and once a week thereafter until Day 56 (i.e. in the mornings of Days 35, 42, 49 and 56); and 2) COVID-19-like illness severity will be assessed at Days 1, 14, 28 and 56 using the categorization from FDA [18] and the Ordinal Scale for Clinical Improvement from the World Health Organization [19]
- Proportion of participants who are "alive and not admitted to the hospital" at Days 1, 14, 28 and 56
- Proportion of participants who visit the emergency room at Days 1, 14, 28 and 56
- Outcome of COVID-19-like illness (hospitalization or death) at Days 1, 14, 28 and 56
- Glucose homeostasis if the participant has T2DM: fasting blood glucose will be measured in the mornings from Day 1 to Day 28 or until they recover from COVID-19-like illness (whichever is later) and weekly thereafter until Day 56

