## D. Endpoints

- 1. Primary outcome:
  - Gut microbiota composition
- 2. Secondary outcomes:
  - At Days 1, 14, 28 and 56:
  - a) Outcome of COVID-19-like illness (hospitalization or death)
  - b) Proportion of participants who are "alive and not admitted to the hospital"
  - c) Proportion of participants who visit the emergency room
  - d) Proportion of participants who have complete resolution of all objective symptoms, i.e. all vital signs are within the normal range for at least 48 h, including body temperature (oral) 36.5-37.5°C (97.7-99.5°F), pulse rate 60-100/min, respiratory rate 12-20/min and oxygen saturation level at 95-100%
  - e) Proportion of participants who have complete resolution of subjective symptoms, i.e. absence of all COVID-19-like symptoms listed by CDC (updated May 13, 2020) for at least 48 h, including the presence of chills or "feeling feverish", cough, shortness of breath or difficulty breathing, fatigue, muscle or body aches, headache, new loss of taste or smell, sore throat, congestion or runny nose, nausea or vomiting and diarrhea
  - f) Proportion of participants who have complete resolution of subjective symptoms except fatigue and cough, i.e. absence of all COVID-19-like symptoms listed by CDC (updated May 13, 2020) for at least 48 h, including the presence of chills or "feeling feverish", cough, shortness of breath or difficulty breathing, fatigue, muscle or body aches, headache, new loss of taste or smell, sore throat, congestion or runny nose, nausea or vomiting and diarrhea
  - g) Illness severity based on the categorization from FDA [18] and the Ordinal Scale for Clinical Improvement from the World Health Organization [19]
  - h) Body temperature (oral)
  - i) Oxygen saturation level
  - i) Pulse rate
  - k) Respiratory rate
  - I) Fasting blood glucose
  - Time to complete resolution of all objective symptoms
  - Time to complete resolution of all subjective symptoms
  - Time to complete resolution of all subjective symptoms except fatigue and cough

Protocol Title: COVGUT20

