#### 6.0 Data Management Plan

#### 6.1 Data Analysis

DNA, protein, and metabolites will be extracted from fecal samples. 16S rRNA gene V4 region sequencing and metagenomic shotgun sequencing with different platforms such as Ilumina and PacBio will be done using the extracted DNA. Metaproteome profiling will be achieved using mass spectrometry-based proteome analysis based on extracted protein. Metabolomics will be measured using fecal sample supernatant. Multiomics data will be combined with clinical data for statistical analysis to explore the overall changes during COVID-19 course and changes induced by the treatment.

16S rRNA gene sequencing data will be analyzed based on the amplicon sequence variants (ASVs) [28] to determine the gut microbiota composition using QIIME 2 [29]. Shannon index and ASV richness will be used to assess alpha diversity. Principal coordinate analysis will be used to compare and visualize dissimilarity in gut microbiota structure between samples based on beta diversity (Weighted and Unweighted UniFrac distance) and statistical differences will be tested using permutational multivariate analysis of variance (PERMANOVA). PICRUSt 2 will be used to predict the functions of individual ASVs and the collective functions of the gut microbiota at the gene content and pathway levels [30]. Global functional profiles of the gut microbiota will be compared and visualized by principal component analysis.

Metagenomic sequencing data will be analyzed in a genome-centric way. The raw sequencing data will be processed with KneadData (https://huttenhower.sph.harvard.edu/kneaddata) for quality control. High quality draft genomes will be de novo assembled from the high-quality sequencing data. The quality assessment, taxonomic assignment and functional annotation of the genomes will be conducted by using CheckM [31], GTDB-Tk [32] and Prokka [33] respectively. Principal coordinate analysis will be used to compare and visualize dissimilarity in gut microbiota structure between samples based on beta diversity and statistical differences will be tested using permutational multivariate analysis of variance (PERMANOVA).

Protocol Title: COVGUT20

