Metagenomic sequencing data will be analyzed in a genome-centric way. The raw sequencing data will be processed with KneadData (https://huttenhower.sph.harvard.edu/kneaddata) for quality control. High-quality draft genomes will be de novo assembled from the high-quality sequencing data. The quality assessment, taxonomic assignment, and functional annotation of the genomes will be conducted by using CheckM [4], GTDB-Tk [5], and Prokka [6] respectively. The principal coordinate analysis will be used to compare and visualize dissimilarity in gut microbiota structure between samples based on beta diversity, and statistical differences will be tested using permutational multivariate analysis of variance (PERMANOVA).

The metaproteomes will be analyzed by using Unified Human Gastrointestinal Genome (UHGG) v2.0 as the reference for functional annotation and protein sequences database. The predicted protein sequences from metagenomic dataset will be aligned with the measured protein sequences from metaproteomic dataset for integrative analysis. Global level protein changes of the gut microbiota will be compared and visualized by principal component analysis. The metabolome will measure both polar metabolites and lipids. Global level of compound changes of will be compared and visualized by principal component analysis.

Repeat measures correlation will be used to assess the relationships between ASVs/highquality draft genomes [7], followed by ASV/high-quality draft genome clustering based on co-abundance patterns. Multivariate methods such as MaAsLin2, that allow adjustment for confounding variables and model the covariates as random effects, will be applied to interpret the relationship between ASVs / ASV co-abundance groups/functions/high-quality draft genome co-abundance groups and the clinical metadata/proteins/metabolites.

Clinical Data Analysis

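### The plan's only power figure is for PERMANOVA on weighted Jaccard distance in confirmed cases, but the planned 16S test uses UniFrac and no analysis set matches those cases

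*Protocol*

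**What the plan says.** **Power.** Protocol section 1.5 rests on a micropower simulation in which "the weighted Jaccard distance matrix was simulated based on within-group distance variance (mean and standard deviation) of data from 36 T2DM patients". It reports: "Our results show that 16 subjects per group afford 80% power" at an omega-squared of 0.0106, and relates this to a value of 0.0120 seen in T2DM patients after a similar intervention. It continues: "We therefore aim to recruit 20 confirmed COVID-19 cases in each group", the excess over 16 being for dropouts and incomplete samples. Enrolment is 50 per group with a positive or pending PCR test, and 40–50% are assumed positive. The SAP contains no power statement.

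**Primary outcome.** Protocol section 1.3 D gives "Gut microbiota composition", without a distance, a day or a contrast. Section 1.3 B says that "fecal samples will be collected at Days 0, 28, 56 and the day when participants recover from COVID-19-like illness (if before Day 56").

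**Planned test.** For 16S data, Protocol section 6.1 compares samples on "beta diversity (Weighted and Unweighted UniFrac distance") and tests differences by PERMANOVA in the same sentence. The SAP names the same two distances in its principal-coordinate sentence and PERMANOVA in the next one. For metagenomic data the SAP compares structure "between samples based on beta diversity, and statistical differences will be tested using permutational multivariate analysis of variance (PERMANOVA"), and names no distance; Protocol section 6.1 does the same.

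**Analysis sets.** Both documents name intent-to-treat and per-protocol datasets and define neither. In the SAP that sentence stands under the heading "Clinical Data Analysis".

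**The concern.** A power figure belongs to a test statistic, an effect size measured on that statistic's scale, and a population. Here the statistic in the calculation differs from the one in the 16S analysis plan, and the population in the calculation has no counterpart among the named analysis sets.

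What is at stake is how the primary result can be read. If the UniFrac PERMANOVA is not significant, nobody can say that the trial had 80% power to find the effect it was sized for, because that figure was never derived for UniFrac. The figure is also the only quantitative justification for the sample size.

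**Working it through.** **1. Can the stated 80% be reproduced?** No. Rerunning the simulation needs the within-group mean and standard deviation of the weighted Jaccard distances, which come from unpublished data and are not given. Section 1.5 also states no alpha; section 6.1 uses 0.05 for each test of an outcome. The 80% can therefore be neither confirmed nor refuted, and nothing here says that it is wrong for weighted Jaccard.

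**2. Do the head counts agree with each other?** Yes.
- Confirmed cases expected per group: 50 × 0.40 = 20, and 50 × 0.50 = 25. The floor of 20 matches the lower positivity rate.
- Loss implied by going from 20 to 16: 1 − 16/20 = 20%. No loss rate is stated.

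**3. Does the 80% transfer from weighted Jaccard to UniFrac?** For a groups and N samples, the PERMANOVA effect size is

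omega-squared = [SS_between − (a − 1) × SS_within/(N − a)] / [SS_total + SS_within/(N − a)].

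Every sum of squares in it is built from squared pairwise distances. Weighted Jaccard compares abundances without a phylogenetic tree. Weighted UniFrac weights abundance differences by branch length. Unweighted UniFrac uses presence or absence along the tree. Changing the distance changes SS_between, SS_within and the spread of the within-group distances. Both inputs to the simulation, the effect size (0.0106, set against 0.0120) and the within-group mean and standard deviation, are thus specific to the distance. The documents give no UniFrac value for any of them, so power under UniFrac is not computable, and its direction relative to 80% is unknown.

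**4. Side by side.**

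| | Power statement (Protocol 1.5) | Planned analysis (Protocol 6.1, SAP) |
|---|---|---|
| Test | PERMANOVA | PERMANOVA |
| Distance, 16S | weighted Jaccard (data type not stated) | weighted and unweighted UniFrac |
| Distance, metagenomic | not addressed | not named |
| Day | not named | not named |
| Population | confirmed cases, 20 per group for 16 evaluable | intent-to-treat and per-protocol, undefined |

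**5. How far apart are the populations?** Objective 1.1 A covers suspected or confirmed patients, so an all-randomized analysis has 50 per group. With the same implied 20% loss that is 50 × 0.80 = 40 evaluable per group, against the 16 in the power statement.

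**The case against.** **The stated purpose is feasibility and exploration (Protocol section 1.1).** True, and it limits the weight of the point. But the plan chose to justify its sample size by a power calculation, and that calculation should describe the test to be run.

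**Sizing on confirmed cases may be conservative.** This largely stands. If the fiber effect on the microbiota is the same in unconfirmed participants (an assumption), an all-randomized analysis has more participants than the calculation used. Some recruitment routes also take people who have already tested positive (sections 1.3 A and 4.1 B), so confirmed cases may exceed 20 per group. Neither fact supplies a defined confirmed-case set, and neither converts a Jaccard figure into a UniFrac one.

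**The powered test might still be performed.** A reader might infer that the plan nowhere runs the test it powered. The documents do not go that far: the metagenomic PERMANOVA leaves its distance open, so weighted Jaccard is not planned there but is not excluded either. The mismatch is shown for 16S only.

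**UniFrac in the SAP is partly inference.** There the distances and PERMANOVA stand in adjoining sentences. The protocol joins them in one sentence, so the natural reading holds.

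**Two further inferences should not carry weight.** One could multiply two UniFrac distances by the post-baseline samples to count competing primary tests. Neither document schedules arm comparisons by day, and the recovery sample exists only for those who recover before Day 56, so the sound statement is simply that no day is named. One could also read the SAP heading as removing the sequencing analyses from the intent-to-treat and per-protocol sets. In the protocol nearly the same sentence closes a single section covering both kinds of analysis, so coverage is unclear rather than denied.

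**Conclusion.** The point holds in this form: the 80% with 16 per group belongs to PERMANOVA on weighted Jaccard distance in confirmed cases, while the planned 16S PERMANOVA of the primary outcome uses UniFrac and no named analysis set corresponds to those cases. The stated power therefore does not apply to the planned 16S tests.

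Its size cannot be given. Without UniFrac effect sizes and spreads, any number would rest on invented inputs. A reader might infer that the trial is underpowered, or that the 80% is miscalculated. The documents support neither: power under UniFrac may be lower or higher, the Jaccard figure cannot be checked, and analysing all randomized participants would raise the numbers.

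The distance mismatch rests on the text alone, with the natural reading of the SAP's two sentences. The remark that sizing on confirmed cases may be conservative rests on an equal effect in unconfirmed participants, which the documents do not establish. This should be corrected, but it does not undermine the design.

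**What to change.** 1. Name one primary PERMANOVA of the arm effect, with one distance, one day (for example Day 28) and one primary population: all randomized participants with an evaluable sample, which fits the objective. Label other distances, other days and the metagenomic PERMANOVA supportive.
2. Match the power statement to it, in one of two ways.
   - Make weighted Jaccard the primary distance, so that the existing calculation applies, with UniFrac supportive. This costs only wording in the protocol and SAP.
   - Keep weighted UniFrac as primary, rerun micropower on it if the 36-patient data allow, and restate the power. If they do not allow it, say in section 1.5 that the 80% applies to weighted Jaccard only and that no power is claimed for the UniFrac tests. This costs one rerun, and the restated power may be less favourable.
3. Define PCR-confirmed participants as a supportive set, and say that the 16-per-group figure refers to that set. This needs the final PCR result of everyone enrolled with a pending test.
4. State in the SAP which analysis sets apply to the sequencing analyses.

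The choice of distance should be made on scientific grounds and fixed before the sequencing data are compared by arm.

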#### 1.6 Study Variables

A. Independent Variables, Interventions, or Predictor Variables NBT-NM108 consumption

## B. Dependent Variables or Outcome Measures

Gut microbiota composition, outcome of COVID-19-like illness (hospitalization or death), proportion of participants who are "alive and not admitted to the hospital", proportion of participants who visit the emergency room at Days 1, 14, 28 and 56, proportion of participants who have complete resolution of all objective symptoms, proportion of participants who have complete resolution of all subjective symptoms except fatigue and cough, time to complete resolution of all objective symptoms, time to complete resolution of all subjective symptoms, time to complete resolution of all subjective symptoms, time to complete resolution of all subjective symptoms except fatigue and cough, COVID-19-like illness severity, body temperature (oral), oxygen saturation level, pulse rate, and respiratory rate

#### 1.7 Drugs/Devices/Biologics

Participants in the treatment group will receive NBT-NM108

They will be asked to prepare each drink

,	ers of diverse physicochemical structures as sources of fermentable carbohydrates for the gut microbiota.
A.	Drug/Device Accountability and Storage Methods

This dosage of NBT-NM108 will provide

## 1.8 Specimen Collection

by mixing one sachet

#### A. Primary Specimen Collection

- Types of Specimens: Each participant will be provided with kits to collect fecal samples at home at each of the following time points: Days 0, 28, 56 and the day when they recover from COVID-19-like illness (if before Day 56). The fecal sample collection kit has been cleared by FDA for at-home use. Instructions and supplies will be provided to collect these samples at home (Appendices 8.1, 8.2 and 16). Participants who have been admitted to the hospital during the study will not collect any samples during hospitalization. If they are discharged on or before Day 56, they will collect a fecal sample at home when they recover from COVID-19-like illness and at Days 28 and 56 as appropriate.
- Annotation: Data to be annotated or associated with each specimen will include participant code, age, sex, ethnicity, medical history, and medication.
- Transport: Participants will return the samples by mailing them to the research team in prepaid shipping boxes. They will either schedule a FedEx pickup or drop off the package at a local FedEx office. The shipping packages are DOT (Department of Transportation) and IATA (International Air Transport Association) compliant.
- Processing: Fecal samples will be processed by Rutgers University research personnel listed in this protocol.
- Disposition: When specimens are no longer in a fit state for scientific analyses, they will be destroyed
  by incineration by authorized research personnel named in this protocol.

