INFORMED CONSENT AND ELIGIBILITY SCREENING PART 2. The informed consent process will be conducted via Castor's eConsent video call module. At the beginning of the call, the study coordinator will confirm that the study candidates continue to experience the COVID-19-like symptoms reported in the preliminary screening survey, thereafter the study coordinator will explain the rationale, aim, expected outcomes and significance of the research, the experimental procedures, what is required from the participants, and the benefits and risks associated with the study. Electronic informed consent will be obtained during the interview prior to further eligibility screening (Appendices 3 and 4). A consent for health information release (Appendix 3) will also be obtained during informed consent procedure. After the study candidates sign the electronic informed consent documents, the study coordinator will ask some additional questions regarding their medical history and other conditions to establish eligibility (Appendix 4). In the case of study candidates who are recruited online, they will also be asked to provide electronic proofs of a positive/pending COVID-19 test (Appendix 24) and a negative pregnancy test result (if appropriate; Appendix 6) during the interview. This consent and eligibility screening interview will take a maximum of 60 minutes to complete.

**ENROLLMENT.** The study physicians will review all screening data and determine if the study candidates are suitable for home isolation and confirm enrollment.

**RANDOMIZATION AND ALLOCATION CONCEALMENT.** Enrolled participants will be randomized to the control or treatment group at a 1:1 ratio, using randomization via a dynamic minimization to minimize imbalance between groups over factors including COVID-19-like illness severity (mild vs moderate), the use of COVID-19 vaccination or other treatments that may reduce severity such as monoclonal antibody treatment vs. not used, age (≤60 vs >60 years) and gender (male vs female) [16]. When imbalance is detected, the new patient will be allocated with probability 0.7 vs 0.3. When the treatment assignments are at balance, the patient will be allocated with probability 0.5 vs 0.5. The randomization will be performed

via a closed source app written by one of the Co-PI. The investigator who uses the app will only know the allocation result, i.e., control or treatment group, of the new patient.

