**SAMPLE AND DATA COLLECTION.** All participants will collect fecal samples at Days 0, 28, 56, and the day when they recover from COVID-19-like illness (if before Day 56). Participants are considered having recovered from COVID-19-like illness when they fulfil the CDC guidelines for discontinuing home isolation for persons with COVID-19 who have symptoms (updated July 20, 2020): at least 10 days have passed since symptom onset, at least 24 h have passed since resolution of fever without the use of fever-reducing medications, and other symptoms have improved. Participants will be provided with supplies and instructions (Appendices 8.1, 8.2 and 16) to collect fecal samples at home using a collection kit developed by

describe the fecal sample on a data collection form based on the Bristol Stool Scale (Appendix 12) [17] and mail the samples and the form to the research team in a prepaid shipping box by following the written instructions in Appendix 18. For participants who require hospitalization during the study, they will collect a fecal sample after they recover (on or before Day 56) and repeat sample collection on Days 28 and 56 as appropriate.

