# C. Subject Screening

# Inclusion Criteria

- Aged between 18 to 79 (inclusive)
- Have mild to moderate COVID-19-like symptoms based on the symptom list from CDC (updated May 13, 2020) and the severity categorization from FDA [18]:
  - a) Mild COVID-19

- Fever or chills, cough, shortness of breath or difficulty breathing, fatigue, muscle or body aches, headache, new loss of taste or smell, sore throat, congestion or runny nose, nausea or vomiting, and diarrhea
- · No clinical signs indicative of moderate, severe, or critical illness severity
- b) Moderate COVID-19
  - Symptoms of moderate illness with COVID-19 could include any symptom of mild illness or shortness of breath with exertion
  - Clinical signs suggestive of moderate illness with COVID-19, such as respiratory rate ≥ 20 breaths/min, oxygen saturation level > 93% on room air at sea level, heart rate ≥ 90 beats/min
  - No clinical signs indicative of severe or critical illness severity.
- Directed to home isolation by study physician

\_

- Practice acceptable contraception, i.e., continue with current methods if participants are already
  practicing contraception, otherwise parti cipants must agree to practicing contraception with a
  barrier method (male or female condom) or abstinence, from Day 1 to Day 35 or 7 days after the
  last dose of NBT-NM108 if they do not complete the 28-day intervention.
- Have access to a smartphone, tablet, computer, or other qualifying internet-enabled device and daily internet access
- Understand and be able to follow written and oral instructions in English
- Provide informed consent

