#### B. Compensation/Incentives

Participants will receive compensation of up to \$100.00, which will be paid in the form of a USF ClinCard if they are recruited from the USF COVID testing center or in the form of reward cards if they are recruited online. The stipend will be available to the participants within one week after they successfully reach the following milestones:

- \$25.00 after the completion of sample collection and shipment at Day 0
- \$25.00 after the completion of sample collection and shipment at Day 28
- \$25.00 after the completion of sample collection and shipment at Day 56, and an additional \$25.00 if the participants successfully complete sample collection and shipment at all time points (including sample collection and shipment at the day of recovery, if applicable)

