#### C. Risks of Harm to Non-Subjects

Protocol Title: COVGUT20

Fecal sample collection at home may impose inconvenience for individuals in the same household.

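### The stool-parcel instruction lets participants still in home isolation use a FedEx office drop-off, most plausibly at Day 0, and the risk sections do not mention it

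*Protocol*

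**What the plan says.** The Transport item of Protocol section 1.8 A gives participants two ways to return samples: "They will either schedule a FedEx pickup or drop off the package at a local FedEx office". The same section covers all four collection points (Days 0, 28 and 56, and the day of recovery if before Day 56). It does not separate them by isolation status or say who may carry the parcel.

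Other sections describe the participant's status when the first parcel is sent:

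- **Entry (4.1 C, Inclusion Criteria):** "Directed to home isolation by study physician". Under Enrollment in 1.3 A, study physicians "determine if the study candidates are suitable for home isolation and confirm enrollment".
- **Consent call (1.3 A):** "the study coordinator will confirm that the study candidates continue to experience the COVID-19-like symptoms".
- **Recovery (1.3 A, Sample and Data Collection):** participants count as recovered when "they fulfil the CDC guidelines for discontinuing home isolation for persons with COVID-19 who have symptoms". The text spells this out as a minimum of 10 days from onset, 24 hours free of fever without antipyretics, and improvement in other symptoms.
- **Timing (1.3 A, Interventions):** supplies go out overnight once the participant is enrolled and randomized, and the intervention starts on Day 1.
- **Payment (4.6 B):** $25 is paid "after the completion of sample collection and shipment at Day 0".

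On risk to others, section 4.7 C has one entry: "Fecal sample collection at home may impose inconvenience for individuals in the same household". The item for other foreseeable risks in 4.7 A is marked not applicable. The SAP does not deal with transport.

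**The concern.** The trial enrolls people because a physician has told them to stay at home with a suspected or confirmed infection. It then offers them, without qualification, a way of returning the first sample that involves visiting a public counter. If a participant takes that option before isolation ends, the trip arises from a study procedure, and the people exposed are courier staff and members of the public who have not consented to anything. An ethics committee or monitoring board reading the risk sections would not learn of this, because the only stated risk to non-subjects is inconvenience in the household.

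**Working it through.** The plan gives no figure for this point, so the check sets the sections side by side and adds some day arithmetic.

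**Step 1: is a participant isolating at Day 0?** Entry requires direction to home isolation, and the consent call confirms continuing symptoms. Recovery is defined as meeting the criteria for ending isolation. By the protocol's own terms, then, a participant who has not recovered is still isolating.

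**Step 2: how much isolation remains at Day 0?** Let d be the days from symptom onset to Day 0. Under the 10-day minimum, remaining isolation is at least 10 − d days. The documents do not give d. Assuming values from 2 to 9:

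- d = 2: at least 10 − 2 = 8 days remain
- d = 9: at least 10 − 9 = 1 day remains
- d of 10 or more: isolation lasts until the fever and improvement criteria are also met

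A participant outside isolation at Day 0 would already satisfy the definition of recovery when entering the trial. That is possible, since symptoms can persist yet be improved, but it would be unusual in a trial of early treatment.

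**Step 3: the other collection points.**

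- *Recovery day:* falls, by definition, when the isolation criteria are met.
- *Days 28 and 56:* onset precedes Day 0, so more than 28 days have passed and the 10-day minimum is satisfied. Only the fever or improvement criteria could still be open, so these parcels normally fall after isolation.

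The point therefore rests on Day 0.

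**Step 4: how many parcels?** With 100 participants planned (section 4.3), up to 100 Day 0 parcels fall under the unrestricted option. The number of trips made by isolating participants would be

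100 × (share isolating at Day 0) × (share of those choosing drop-off) × (share of those carrying the parcel themselves).

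The documents give none of the three shares, so the result can only be bounded between 0 and 100.

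**Step 5: does a stated safeguard cover the trip?** The measures in section 4.7 E (sealed container, leak-proof secondary package, outer box) and the transport compliance statement in 1.8 A protect against the specimen. None concerns the participant's own contact with others on the way to the office or at the counter.

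**The case against.** The strongest reply is that the two instructions can both be followed. Pickup is named first and is compatible with isolation, and nothing in section 1.8 A lifts the direction to isolate. A reader might infer that the protocol sends infectious participants out of isolation, or flatly contradicts its entry criterion. The text does not support that: it permits a breach and does not require one. Drop-off also has a legitimate use at the later collection points. What stands against this reply is that the option is not confined to those points.

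Several other stronger readings also fail:

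- **Payment as an inducement to leave home.** The $25 is earned by shipment through either route, so it does not favor drop-off.
- **The contact-minimizing aim in section 4.4 B.** That sentence justifies the altered consent process and concerns research personnel. It is not a general commitment covering couriers or the public.
- **A count of trips by infected participants.** The 40-50% positivity in section 1.5 is assumed for the USF drive-through center. It does not carry over to all recruits, since those coming through Vault Health have already tested positive. No drop-off share is given anywhere.
- **All, or nearly all, Day 0 parcels fall in isolation.** No maximum time from onset to enrollment is visible, and one inclusion bullet is blank in the available text. Only the word usually can be defended.

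Finally, section 1.3 A refers participants to Appendix 18 for shipping instructions. It is not among the documents and may already require pickup during isolation. If so, the remaining defect is that section 1.8 A does not say so.

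**Conclusion.** The concern holds as a procedural inconsistency with a safety aspect. Section 1.8 A leaves drop-off open at all times, although the Day 0 parcel will usually be sent while the participant is isolating, and the risk sections omit the possible exposure of others. This conclusion rests on two assumptions: that Day 0 follows enrollment closely, as the overnight shipment and Day 1 start imply, and that most participants enroll before meeting the criteria for ending isolation.

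Its size is limited. Up to 100 Day 0 parcels are covered by the option, but the number of trips is unknown and the pickup route avoids the problem entirely. Endpoints, power, randomization and analysis are unaffected.

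**What to change.** Reconcile section 1.8 A with the isolation criterion in 4.1 C and the recovery definition in 1.3 A. State that any parcel sent before the participant meets the criteria for ending isolation goes by the FedEx home pickup already offered, and that drop-off is available only afterwards. Check Appendix 18 and make it match. In section 4.7 C, name the risk to people outside the household and this control, and bring the corresponding item in 4.7 A into line.

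Handing the parcel to another household member is not a clean substitute, because that person may be a close contact of a suspected case.

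The change takes a few sentences and no new service, and alters no sample time, endpoint or payment. The cost is a possible short delay in the dispatch of some Day 0 parcels while a pickup is arranged.
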